## 6.11.6 Supplementary Analyses

Analysis of Section 6.11.2 will be repeated for the Per Protocol population.

Additional analysis will investigate the treatment effect on PRO TSS change from baseline in the subgroups defined in Section 5.9. This analysis will use MMRM similarly to the primary analysis (Section 6.11.2).

Empirical cumulative distribution function (eCDF) of the change from baseline in TSS will be plotted by treatment group to demonstrate consistency of the treatment effect.

## 6.12 Analysis of Secondary Efficacy Endpoints

### 6.12.1 Change in Tissue Eosinophil Count

For subjects who provide duodenal biopsy, the calculation will be based on the average count of the highest readings from the respective mucosa at baseline and Day 169 (Week 24). The change in tissue eosinophil count from baseline to Day 169 will be analyzed using ANCOVA with treatment as factor, baseline eosinophil counts, baseline PRO TSS as covariates. The LSM, SE, and 95% CI for individual treatment groups, and LSM, SE, 95% CI, and p-value for the between treatment difference will be presented.

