In the randomized, double-blind, placebo-controlled, Phase 2 study of AK002 in 65 patients with EG and/or EoD, patients were randomized to receive monthly doses of placebo, low dose AK002 (0.3, 1, 1, and 1 mg/kg), or high dose AK002 (0.3, 1, 3, and 3 mg/kg) in a 1:1:1 ratio. All primary and secondary endpoints were met in the study. There was a 97% and 92% mean reduction in eosinophils in the stomach/duodenum for the high dose and low dose AK002-treated patients, respectively, vs a 10% increase for placebo-treated patients ($p<0.0001$). There was also a statistically significant reduction in total symptom score (TSS) of 58% in the high dose AK002 group and 49% reduction in the low dose group AK002 vs a 24% reduction in the placebo group ($p=0.0012$ and $p=0.015$, respectively). Improvement in symptoms were observed within 24 hours of the first dose of study drug. In addition, 70% of high dose treated patients and 68% of low dose treated patients were treatment responders (defined as $>30\%$ improvement in TSS and $>75\%$ reduction from baseline in tissue eosinophils) vs 5% of placebo-treated patients ($p<0.0001$) ([Dellon, 2020](#)).

Among the 65 patients, there were patients with EG without EoD, patients with EoD without EG, and patients with both EG and EoD, and these subgroups had similar symptoms and symptom severity. The treatment benefit of AK002 was observed across all of the subgroups, whether eosinophilia was reported in the duodenum with or without concomitant EG.

Patients with EoD without EG had a similar histologic response on AK002 treatment as those with EG with or without EoD (All EG). AK002 resulted in a -99.5% and -91.5% mean change in tissue eosinophils in patients with EoD without EG and in patients with EG ± EoD, respectively. The proportion of patients achieving ≤ 1 eosinophil/hpf at the end of treatment was also similar (93.3% and 75% of EoD without EG and All EG, respectively), compared to no patients on placebo. Additionally, symptomatic improvement was similar; EoD without EG patients had a mean change in TSS of -57.4%, and all EG patients experienced a -51% mean change in TSS.

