4.5.5 Strategy for Handling Intercurrent Events

For the analysis of the trial product estimand, tissue eosinophil values and TSS will be counted as non-responders for binary variables and set to missing for continuous outcomes from the point when an ICE occurs. An appropriate method for handling missing data through statistical modeling, e.g., multiple imputation (MI) will be used. The estimand will provide an answer to the question that is crucial to individual subjects, “If I take this study medication as part of my treatment regimen, without adding any further medications that may impact the underlying disease or exit the study prematurely, what improvements in histology and PRO symptoms might be anticipated after 24 weeks?”

5. Study Design

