## 2.2 Secondary Objectives – Secondary Endpoints

The secondary objectives are to characterize further the efficacy of AK002 in subjects with EoD as measured by:

- Percent change in tissue eosinophils from baseline to Week 24
- Proportion of subjects achieving mean eosinophil count  $\leq 1$  cell/hpf in 3 highest duodenal hpf at Week 24
- Proportion of treatment responders at Weeks 23- 24. Responder is defined as  $>30\%$  improvement in TSS symptom score **and** mean eosinophil count  $\leq 15$  cells/hpf in 3 highest duodenal hpf
- Proportion of subjects who achieve  $\geq 50\%$  reduction in TSS from baseline to Weeks 23–24
- Proportion of subjects who achieve  $\geq 70\%$  reduction in TSS from baseline to Weeks 23–24
- Percent change in weekly TSS over time

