### 5.4 Handling of Dropouts, Missing Data, and Data Discrepancies

#### 5.4.1 Missing Duodenal Tissue Eosinophil Count at Week 24

Eosinophil counts will be set to missing if they are collected after subjects have experienced ICE. Subject with missing Week 24 tissue eosinophil count for any reason will be imputed with the eosinophil count collected from the postbaseline unscheduled visit prior to missing. If no eosinophil count is collected postbaseline, the subject will be considered treatment failure for tissue eosinophil response.

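### The common-variance ANCOVA for tissue eosinophil change will give misstated arm-level confidence intervals: too narrow for placebo, too wide for AK002. The gated test is not threatened.

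*SAP*

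**What the plan says.** SAP 6.12.1 states: "The change in tissue eosinophil count from baseline to Day 169 will be analyzed using ANCOVA with treatment as factor". The covariates are the baseline eosinophil count and the baseline TSS. It names no treatment-by-baseline term, arm-specific variance, transformation or robust standard error. The committed output is: "The LSM, SE, and 95% CI for individual treatment groups, and LSM, SE, 95% CI, and p-value for the between treatment difference will be presented".

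This is the first endpoint in the secondary hierarchy (SAP 5.8, which takes its order from SAP 2.2). SAP 2.2 lists it as "Percent change in tissue eosinophils from baseline to Week 24", as does Protocol 4.2. SAP 6.12.1 and Protocol 6.2.2 speak of change, not percent change.

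Protocol 2.3 gives the expected pattern. In Phase 2 patients with EoD without EG, AK002 produced a mean change of -99.5%, and 93.3% reached at most 1 eosinophil/hpf, "compared to no patients on placebo". Phase 2 placebo patients as a whole (stomach/duodenum) rose by 10%.

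On missing counts, SAP 5.4.1 deletes values collected after an intercurrent event. It then fills a missing Week 24 count from an earlier unscheduled post-baseline count. If there is none, "the subject will be considered treatment failure for tissue eosinophil response". SAP 6.12.1 opens with "For subjects who provide duodenal biopsy, the calculation will be based on the average count of the highest readings" and names no imputed data set. Protocol 4.5.5 says: "An appropriate method for handling missing data through statistical modeling, e.g., multiple imputation (MI) will be used". SAP 4.2.5 does not repeat that sentence.

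**The concern.** An ordinary ANCOVA estimates one residual SD from both arms and uses it for each arm's SE. If almost every AK002 patient ends near zero, AK002 contributes almost no residual spread on the percent scale. On the raw scale its change is nearly minus the baseline count. Placebo keeps its full biological and sampling variation. The pooled SD then lies between the two and is wrong for both arms.

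What is at stake is the arm-level error bars of the first secondary endpoint. The placebo mean would look more precise than it is and the AK002 mean less precise. If the arms are unequal in size, the interval for the difference is affected too. The Evaluable population makes unequal arms possible: it is carved out of about 80 randomized patients by two baseline criteria that are not stratification factors, and the documents give no expected size by arm.

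**Working it through.** **The plan's own figure.** SAP 6.12.1 states no power, SD or N. The only stated figure on tissue eosinophils is power above 90% for responder rates of 0.6 vs 0.1 with 40 per arm (SAP 3.5). Check: the pooled rate is 0.35. The null SE is sqrt(2 x 0.35 x 0.65 / 40) = 0.1066, and the alternative SE is sqrt((0.24 + 0.09) / 40) = 0.0908. Then z = (0.5 - 1.96 x 0.1066) / 0.0908 = 3.2, which gives 99.9% power. Exact enumeration of Fisher's test gives 99.8%. The statement holds.

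**Analytic limit for the interval.** Let the placebo residual SD be s and the AK002 residual SD be 0, with equal slopes.
- At 1:1, the pooled SD = s x sqrt(1/2) = 0.71s. The nominal 95% placebo interval is 0.71 of its proper width. Its coverage is 2 x Phi(1.96 x 0.707) - 1 = 83.4%, whatever s is.
- At 34 AK002/26 placebo, the pooled SD = s x sqrt(26/60) = 0.658s. Coverage is 2 x Phi(1.96 x 0.658) - 1 = 80.3%.

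**Simulation inputs.** From the documents: the baseline floor of 30/hpf, 40 per arm, AK002 at or below 1/hpf in 93.3%, placebo at 1.1 x baseline. Assumed, because no SDs are given: baseline mean 60/hpf, baseline SD 15-30, placebo CV 0.2-0.6, 2,500-4,000 runs per setting. Arm-level coverage refers to the mean at the trial's own average baseline, which is what an LSM estimates.

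**Results for the planned ANCOVA, raw change.**

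| Setting | Placebo CI | AK002 CI | CI for difference |
|---|---|---|---|
| 40/40, CV 0.2 | 89.9-93.1% | 98.6-99.9% | 92.0-94.3% |
| 40/40, CV 0.4 | 86.3-87.3% | 99.7-100% | 91.6-94.6% |
| 40/40, CV 0.6 | 84.1-85.0% | 99.9-100% | 92.6-93.5% |
| 34 AK002/26 placebo, CV 0.4 | 83.6% | 99.9% | 89.3% |
| 26 AK002/34 placebo, CV 0.4 | 89.8% | 99.7% | 94.5% |

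A further run at CV 0.3-0.5, on both the raw and the percent scale, gave 79-86% for placebo, 99-100% for AK002, and 88-91% for the difference at 34/26. The low end for placebo fits the 80.3% limit above.

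**Under the planning rate.** If only 60% of AK002 patients reach 15/hpf, AK002 has real spread. Placebo coverage is then about 86-95%, and the AK002 interval is 1.3-1.8 times too wide.

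**The gated test.** With no treatment effect the two arms share one distribution, so pooling is correct. Simulated type I error was 5.3% at 40/40 and 4.9% at 34/26. Power was 100% in every scenario under the Phase 2 pattern.

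**Possible repairs.** Separate slopes and model-based variances per arm restore placebo coverage to about 92-95%. They leave AK002 at about 80-87% (84.1-85.8% at 40 per arm, 78.5% in the 26/34 run), because the near-zero counts are skewed. HC3 errors on the planned ANCOVA gave 92-95% for placebo and for the difference. For AK002 they gave 97-100% under the Phase 2 pattern and 93-96% under the planning rate.

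**The case against.** The strongest reply is that nothing decision-relevant is affected. The hierarchy turns on the between-arm test, which keeps its level and has ample power, and the AK002 error is conservative. That stands, and it sets the weight of the point. It does not excuse the placebo interval, which is too narrow, or the interval for the difference when the arms are unequal.

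A second reply is that the size rests on assumed SDs and on Phase 2 repeating. This also stands, which is why a range is given and why the planning-rate result is shown beside it.

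A third is that SAP 5.1 allows alternative methods before database lock if assumptions fail. It names none, so it mitigates without settling the matter.

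A reader might also infer that patients with intercurrent events are simply dropped, against the estimand. The documents do not support that. SAP 5.4.1 first carries forward an unscheduled post-baseline count, so only patients without one lack a rule for the continuous endpoint. The estimand in Protocol 4.5.5 and SAP 4.2.5 asks what would happen without added medication or early exit, which is a hypothetical question. With one post-baseline biopsy and the same covariates, complete-case ANCOVA under MAR targets the same quantity as MAR multiple imputation. In a check with 40 per arm and 12% missing at random, the difference was -65.4 complete-case, -65.4 with imputation and -65.5 with full data. Protocol 4.5.5 offers imputation only as an example, and the SAP supersedes the protocol's statistical methods.

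**Conclusion.** The point holds as an estimation and reporting error. If Phase 2 repeats, the nominal 95% interval covers about 79-86% for placebo and 99-100% for AK002. Under the 60% planning rate, placebo coverage is about 86-95%. The difference is covered about 93-94% at 40/40 and about 88-91% at 34/26. These figures assume a baseline mean of 60/hpf and a placebo CV of 0.3-0.5. Over the wider grid at 40/40, placebo coverage was 84-93% and coverage of the difference 91.6-94.6%. Under the Phase 2 pattern the direction was the same in every scenario.

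A reader might infer that the first step of the secondary hierarchy is invalid. It is not: type I error is about 5% and power about 100%.

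The scale must be settled first. On the percent scale the AK002 slope on baseline largely disappears, but the unequal variance remains, so the point survives either choice. The missing-count gap is a matter for clarification and is not shown to bias the stated estimand.

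**What to change.** In SAP 6.12.1:

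1. State whether percent change or change is analysed, and make SAP 2.2 and Protocol 4.2 and 6.2.2 agree with it.
2. Keep the planned ANCOVA, but compute the SEs, CIs and p-value with the HC3 estimator, (X'X)^-1 X' diag(e_i^2 / (1 - h_ii)^2) X (X'X)^-1, for each arm and for the difference. Do not rely on arm-specific slopes with model-based variances, because the AK002 interval then under-covers. If raw change is chosen, say that the arm intervals refer to the mean at the trial's average baseline. On that scale HC3 does not allow for sampling variation in the AK002 baseline itself.
3. State how patients with no usable post-baseline count enter the continuous analysis.

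The cost is a few lines of SAP text and code, and a wider, less favourable placebo interval: up to 1/0.71 = 1.4 times the planned width in the limiting 1:1 case. Neither the design nor the order of testing changes.

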### 6.12.2 Proportion of Subjects Achieving Peak Duodenal Intraepithelial Eosinophil Count of $\leq 1$ Cell/hpf

This endpoint will be analyzed using the Fisher's exact test similar to the analysis for the first co-primary endpoint (Section 6.11.1).

### 6.12.3 Proportion of Treatment Responders

Treatment responder is defined as  $>30\%$  improvement in TSS and mean eosinophil count  $\leq 15$  cells/hpf in 3 highest duodenal hpf. This endpoint will be analyzed using Fisher's exact test similar to Section 6.11.1.

### 6.12.4 Proportion of Subjects with $\geq 50\%$ Reduction and $\geq 70\%$ Reduction in TSS from Baseline to Weeks 23–24

These 2 endpoints will be analyzed using the CMH test stratified by the randomization stratification factor.

### 6.12.5 Change in Weekly TSS Over Time

Prior to the analysis, the missing weekly TSS scores will be imputed similarly to the imputation for the missing biweekly PRO TSS scores (Section 5.4.2). The imputed data sets will be analyzed using the mixed model for repeat measures (MMRM) similar to the analysis for the second co-primary endpoint.

The rationale for using the MMRM model is that this analysis is appropriate assuming subjects with missing data behave similarly to other subjects in the same treatment group. Having included in the model baseline symptom score (TSS), and response trajectory prior to missing, it is reasonable to believe that the missing data are either completely at random (MCAR) or at random (MAR) in this setting. In another words, if missing mechanism is not MCAR, it is likely explainable by the above model covariates and response trajectory.

## 6.13 Analysis of Exploratory Endpoints

### 6.13.1 Change in

Change from baseline in the number of  
will be analyzed using

in **CCI**

### 6.13.2 Change in

Change from baseline in summary (including domain scores) will be analyzed using

similar to Section 6.12.5.

### 6.13.3 Change in

Change from baseline in will be analyzed using

#### 6.13.4 Change in [REDACTED]

Changes in [REDACTED] from baseline compared to post-treatment in the [REDACTED]

[REDACTED] will be analyzed using

#### 6.13.5 [REDACTED]

Change from baseline in [REDACTED]

[REDACTED] will be analyzed using the [REDACTED] similar to the [REDACTED]

- [REDACTED]
- [REDACTED]
- [REDACTED]
- [REDACTED]
- [REDACTED]
- [REDACTED]

[REDACTED] the analysis variable, will be based on the [REDACTED]

[REDACTED] and calculated as the [REDACTED]

[REDACTED] to establish a [REDACTED]

[REDACTED] The data will be analyzed by [REDACTED] at

Weeks 23-24. The sample SAS code follows.

[REDACTED]

[REDACTED]

[REDACTED]

[REDACTED]

• [REDACTED], the analysis variable, will be the [REDACTED]  
(defined as [REDACTED] and calculated as the [REDACTED]  
[REDACTED] to establish a [REDACTED] Analyzed in a [REDACTED]

### 6.13.6 **CCI** and **CCI**

Methods for **CCI** and **CCI** are described in a separate analysis plan.

## 6.14 Analysis of Pharmacokinetic Endpoint

The analysis of the PK concentration will be based on the Safety population. AK002 concentrations will be listed by treatment, subject, nominal time, and actual time. Concentrations that are below limit of quantification (BLOQ) will be indicated in the listing.

Plasma concentrations will be summarized at each nominal time point separately for each treatment. The following descriptive statistics will be presented: n, arithmetic mean, SD, geometric mean, % CV, median, minimum, and maximum.

Individual plasma concentration vs. actual times will be plotted for each subject in linear and semi-logarithmic scales, placed on the same page. Mean plasma concentration at the scheduled time points will be plotted for each treatment in linear and semi-logarithmic scale, with the associated standard errors (for linear scale only) at each scheduled time point.

In the plot, concentrations that are BLOQ will be assigned a value of 0 if they are collected predose or assigned a value of 1/2 the lower limit of quantification (LLOQ) if they are collected postdose.

Analysis of PK parameters are specified separately in a PK analysis plan.

## 6.15 Safety Analyses

### 6.15.1 Adverse Events

Safety assessments will be based mainly on the nature, frequency, relationship, and severity of adverse events (AE). The AE will be coded by primary System Organ Class (SOC) and Preferred Term (PT) according to MedDRA (version 21.0). The treatment-emergent adverse events (TEAE) will be summarized by the number and percentage (n and %) of subjects in each SOC and PT.

For summaries by relationship to study drug, “possibly related” will be combined with “related”, and “unlikely/remotely related” will be combined with “not related.” When multiple AE are reported with the same PT, the AE of the strongest relation to study drug will be included in the summary by relationship, and the AE of the most severe grade will be included in the summary by severity table.

The following AE incidence tables will be presented.

- Overview of TEAE to include
  - Number (%) of subjects who reported at least 1 TEAE
  - Number (%) of subjects who reported at least 1 treatment-related TEAE
  - Number (%) of subjects who reported at least 1 severe TEAE
  - Number (%) of subjects who reported at least 1 serious TEAE
  - Number (%) of subjects who reported at least 1 TEAE leading to treatment discontinuation
  - Number (%) of subjects who reported at least 1 TEAE leading to study discontinuation
  - Number (%) of subjects who reported at least 1 TEAE of special interest (TEAESI)
- TEAE by PT sorted by decreasing order of subject incidence in the combined treatment group
- TEAE by SOC and PT in alphabetical order
- TEAE by SOC, PT, and maximum severity
- TEAE by SOC, PT, and strongest relationship to study drug
- TEAE leading to treatment discontinuation by SOC and PT, if warranted by sample size
- TEAE leading to study discontinuation by SOC and PT, if warranted by sample size
- Serious TEAE by SOC and PT, if warranted by sample size
- TEAESI by SOC and PT

All AE will be listed with onset/stop day, relationship to study drug, severity, action taken, and outcome. Pertinent subject information including treatment group and demographics will also be included.

Separate listings will be provided for TEAE leading to study discontinuation, TEAE of special interest, and treatment-emergent serious AE (TESAE).

### 6.15.2 Laboratory Test

Laboratory data will be summarized by presenting summary statistics of raw data and change from baseline values (means, medians, standard deviations, ranges). For quantitative laboratory parameters, both actual values and change from baseline values will be summarized at each visit.

Shift tables will be presented, in which, lab test results at baseline and post-baseline visit will be classified into below ( $<\text{LLN}$ ), within ( $\geq\text{LLN}$  and  $\leq\text{ULN}$ ), and above ( $>\text{ULN}$ ) normal ranges. Subject incidences (n and %) will be presented for the shift from baseline to the post-baseline visits.

Note that the analysis window will be applied for the visits.

A complete laboratory data listing, including hematology, biochemistry, and urinalysis will be provided for all subjects.

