15.7.3 Clinical Laboratory Assessments

Samples will be obtained for the clinical laboratory tests identified in Section [11.4](#), and laboratory tests to be summarized include chemistry, hematology, urinalysis, and AK002 ADA. Descriptive statistics will be used to summarize laboratory results at baseline, each visit, and the change from baseline for each visit. In addition, shift tables will summarize the laboratory results relative to normal reference ranges at baseline and each post-baseline time point.

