**Table 4 Analysis Window Rules for Vital Sign and Laboratory Tests**

Visit Description	Window
Baseline	On or Prior to Day 1 Predose
Day 1	Day 1 Postdose
Day 15	Day 2 to Day 22
Day 29	Day 23 to Day 42
Day 57	Day 43 to Day 70
Day 85	Day 71 to Day 98
Day 113	Day 99 to Day 126
Day 141	Day 127 to Day 158
Day 176	Day 159 to 186
Day 197	Day 187 to End of Study

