**Table 6 Analysis Window Rules for Blood Histamine and Urinalysis**

Visit Description	Window
Baseline	On or Prior to Day 1 Predose
Day 1	Predose on Day 1
Day 29	Day 1 Postdose to Day 42
Day 57	Day 43 to Day 70
Day 85	Day 71 to Day 98
Day 113	Day 99 to Day 126
Day 141	Day 127 to Day 158
Day 176	Day 159 to Day 186
Day 197	Day 187 to End of Study

In the event of multiple values from unscheduled or early termination assessments within a single analysis window, the value closest to the scheduled visit target study day will be used for analyses. If 2 values tie as closest to the time point (for example, 1 value is before and the other value is after the time point), then the later value will be selected. Data collected at all visits will be included in the data listings with visit presented as reported by the site.

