#### **6.15.3 Vital Signs, Height and Weight, and Other Safety Measures**

Vital signs will be summarized by presenting summary statistics of raw data and change from baseline values (means, medians, standard deviations, ranges) for each visit (per analysis window) and time point. A data listing will include vital signs from all visits.

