Table 14.3.1.8b	Treatment-Emergent Adverse Events of Special Interest by System Organ Class and Preferred Term: Subject Incidence (Evaluable Population)
Table 14.3.2.1	Hematology: Change from Baseline by Visit (Safety Population)
Table 14.3.2.2	Blood Chemistry: Change from Baseline by Visit (Safety Population)
Table 14.3.2.3	Hematology: Shift from Baseline Classification by Visit (Safety Population)

Table 14.3.2.4      Blood Chemistry: Shift from Baseline Classification by Visit  
(Safety Population)

Table 14.3.2.5      Urinalysis: Change from Baseline by Visit (Safety Population)

Table 14.3.3      Summary of Vital Signs by Visit (Safety Population)

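### No planned table counts patients per arm by worst post-baseline lymphocyte grade, and no rule says which of two scheduled blood counts a visit row reflects

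*SAP*

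**What the plan says.** SAP 6.15.2 plans summary statistics of laboratory values and of their changes at each visit, plus a shift table: "Shift tables will be presented, in which, lab test results at baseline and post-baseline visit will be classified into below" the lower limit of normal, within range, or above the upper limit. It adds: "Note that the analysis window will be applied for the visits". In SAP Appendix 3 the hematology tables are 14.3.2.1 (change from baseline by visit) and 14.3.2.3, titled "Hematology: Shift from Baseline Classification by Visit (Safety Population"). A full laboratory listing is also planned. No graded or worst-value laboratory table is listed.

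SAP Table 4 sets the windows for laboratory tests. The first post-baseline row is "Day 1 Postdose". The later rows are Days 15, 29, 57, 85, 113, 141, 176 and 197. The only selection rule, printed after Table 6 in SAP 5.2, concerns "multiple values from unscheduled or early termination assessments within a single analysis window, the value closest to the scheduled visit target study day", which is kept; a tie goes to the later value.

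Vital signs are summarised "for each visit (per analysis window) and time point" (SAP 6.15.3). SAP 6.15.2 mentions the visit only. Protocol 15.7.3 was more specific: "shift tables will summarize the laboratory results relative to normal reference ranges at baseline and each post-baseline time point". The SAP supersedes the protocol on statistical methods (SAP 1).

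SAP 6.15.1 opens: "Safety assessments will be based mainly on the nature, frequency, relationship, and severity of adverse events (AE"). Protocol 10.3 and 11.2.5 withhold the post-dose differential, lymphocytes included, from Investigator and Sponsor until after database lock. The Safety Monitor sees it in real time.

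**The concern.** Protocol 2.3 describes a temporary lymphocyte fall after AK002 infusion in every study, usually over within a day. A Phase 3 report should let a reader see how deep that fall goes and in how many patients per arm. The planned tables can show how many patients were below normal at a visit. They cannot show how many ever reached grade 3 or 4.

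The timing of the draw matters as well. On Days 29 to 141 the predose count comes about four weeks after the previous infusion, when recovery is expected. The 1-hour postdose count is taken when the fall is expected. A single row for the day can describe either state. The Day 1 postdose row is clean, but it follows the only infusion with mandatory 80 mg prednisone. Later infusions have steroid premedication only with the Medical Monitor's approval, so Day 1 need not stand for them.

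The adverse event tables do not fill the gap. Under protocol 11.4 the Investigator decides whether an abnormal value is clinically significant and records it as an AE, yet the Investigator does not see these values.

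**Working it through.** The documents state no figure on this point, so the check is a count of scheduled draws against windows.

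**Draws per patient** (protocol 11.2.5), from Day 1 postdose to Day 225:
- Day 1 postdose: 1
- Days 8 and 15: 2
- predose and 1-hour postdose on Days 29, 57, 85, 113 and 141: 5 × 2 = 10
- Day 169: 1
- Days 176, 197 and 225: 3

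Total: 1 + 2 + 10 + 1 + 3 = 17.

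**Assignment to SAP Table 4:**

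| Row | Window | Scheduled draws |
|---|---|---|
| Day 1 | Day 1 postdose | Day 1 postdose |
| Day 15 | 2–22 | Day 8, Day 15 |
| Day 29 | 23–42 | predose, postdose |
| Day 57 | 43–70 | predose, postdose |
| Day 85 | 71–98 | predose, postdose |
| Day 113 | 99–126 | predose, postdose |
| Day 141 | 127–158 | predose, postdose |
| Day 176 | 159–186 | Day 169, Day 176 |
| Day 197 | 187 to end | Day 197, Day 225 |

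There are nine windows: one holds a single draw and eight hold two (1 + 8 × 2 = 17). Five of the eight mix predose and postdose. The permitted visit windows of ±2 or ±3 days never move a draw into another row. Patients entering the extension skip Days 197 and 225, which leaves 15 draws in 8 windows, 7 of them paired. Chemistry, drawn only predose on dosing days, pairs in just three windows, so the problem is largely one of the blood count.

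**What each possible handling would do:**
- Separate rows by time point: all 17 draws are summarised.
- One value per window: 17 − 9 = 8 draws unused, 8/17 = 47% (extension entrants 15 − 8 = 7, 7/15 = 47%).
- One value per window with the SAP 5.2 rule extended to scheduled draws: the postdose count is kept on dosing days, because the two draws tie on study day. The five predose counts and Days 8, 169 and 225 go unused.
- One value per window with predose chosen: five of the six postdose counts go unused.

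The SAP does not say which applies.

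**Grades.** Protocol Appendix 4 gives lymphocyte grade 1 as below the lower limit of normal down to 800/mm³, grade 2 below 800 to 500, grade 3 below 500 to 200, and grade 4 below 200. The shift table places all four in one level.

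**Why by-visit rows do not give incidence.** Suppose the minimum in an arm lies below 500/mm³ in each of the five dosing-day rows. That could be one patient five times or several different patients. Neither the minima nor the counts below normal can be combined across rows into a number of patients who ever reached grade 3.

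**The case against.** The strongest reply is that most of the information is already planned. SAP 6.15.2 reports ranges, so the lowest summarised count in each arm is visible at each visit, including Day 1 postdose, and the listing holds every value. That stands: what is missing is the number of patients, not sight of extreme values.

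A reader might infer that 47% of the counts are discarded. The documents do not support that. No SAP text drops a scheduled draw; the selection rule names only unscheduled and early termination values. If its tie provision were extended, the dosing-day rows would show the post-infusion counts, although still ungraded. Nor does a by-visit title exclude separate time points: Table 14.3.3 for vital signs has such a title although SAP 6.15.3 summarises by time point. What remains is an undefined choice.

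A reader might also infer that patients are unprotected, or that the AE tables are shown to under-report. Neither follows. Panic alerts go to the Safety Monitor in real time, the Safety Monitor can request extra counts and escalate, and an iDMC meets during the study. Sites may also order additional tests (protocol 11.4). Under-reporting in the AE tables is a reasonable inference from the blind, not something the documents state or quantify.

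Finally, the protocol calls the fall transient and without clinical consequence. Lymphopenia is not an event of special interest, while opportunistic and parasitic infections are, with their own tables. More than 90% of Phase 2 patients continued into the extension study, so 7 of 8 may describe most patients better than 8 of 9. These points limit the importance. They do not supply the missing count.

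**Conclusion.** The point holds as a reporting gap of modest importance. The planned tables cannot give the number of patients per arm by worst post-baseline lymphocyte grade. For the blood count, 8 of 9 windows (7 of 8 for extension entrants) hold two scheduled draws, five of them a predose and a postdose draw, with no stated rule. Depending on how that is resolved, between 0 and 8 of the 17 scheduled counts would stay out of the by-visit tables; the plan does not fix where in that range it falls.

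The count assumes a patient who follows the visit schedule; early terminators have draws at other days. The documents give no grade 3 or 4 rate, so no incidence is estimated here. Data collection, real-time patient safety and the efficacy results are not affected.

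**What to change.** Add to SAP 6.15.2 and to the table list in Appendix 3 one table for the Safety population: the shift from baseline CTCAE v5 lymphocyte grade to worst post-baseline grade, by arm. Use all central laboratory draws, unscheduled ones included, without window selection, and show the 1-hour postdose draws separately from the other draws. Produce it after database lock.

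Two small additions are optional: a sentence in SAP 5.2 saying how two scheduled draws in one window are handled, and a footnote that the AE tables do not reliably capture blinded differential counts.

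The cost is the programming of one table from data already collected. The blind is not touched.
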